5.2. Secondary Outcome Analysis

All secondary outcomes will be analyzed as a superiority design, and two-sided 95% CIs for the differences in these outcomes between two groups will be calculated. Secondary outcome analyses will be based on the ITT population unless specified.

5.2.1 Analysis of binary outcomes

The incidence of CLABSI will be summarized by the number (%) of patients with event by treatment group and analyzed by GLM (the same method as the primary outcome).

The difference of incidence and its two-sided 95% CIs between the two groups will be estimated. If necessary for analysis, odds ratios or risk differences with two-sided 95% CIs of the two groups will be derived from the GLM with binomial distribution, and logit or identity link functions, respectively.

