5.1. Primary Outcome Analysis

5.1.1 ITT analysis of the primary outcome - the primary analysis

The primary outcome is a binary outcome: the occurrence of skin bacterial colonization on the seventh or eighth day after CVC catheterization. The primary analysis will be based on the ITT population as defined above.

Hypothesis: Let π_1 denote the occurrence of skin bacterial colonization on the eighth day after CVC catheterization in the CD24h group (control group), and let π_2 denote the occurrence of skin bacterial colonization on the seventh day in the CD7d group (experimental group), the non-inferiority margin $\Delta=20\%$. The null hypothesis is $H_0: \pi_2 - \pi_1 > \Delta$ versus the alternative hypothesis is $H_A: \pi_2 - \pi_1 \leq \Delta$.

A generalized linear model (GLM) will be used to test the above hypothesis. In the GLM, the occurrence of skin bacterial colonization will be treated as the dependent variable and the treatment as the fixed effect, following a binomial distribution and identity link function. A point estimate of risk difference between groups in the difference and its 95% confidence interval (CI) will be estimated. CD7d treatment will be considered non-inferior to the CD24h treatment if the upper 95% confidence limit is no greater than Δ , where $\Delta= 20\%$, the predetermined non-inferiority margin.

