5.1.2 Sensitivity analyses of the primary outcome

- PP analysis with GLM (described in 5.1.1) will be performed.
- An analysis of the primary outcome will be adjusted for age, gender, CVC catheterization site, type of disease, and administration set at baseline in ITT and PP population, respectively. The adjusted difference and 95% one-sided upper limit comparing the two groups will be derived by GLM (described in 5.1.1). If the above identity-binomial GLM does not converge when all covariates are introduced into the model, the adjusted model will be performed by removing a covariate one by one until the model converges.

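### The SAP gives CLABSI the primary outcome's identity-link GLM, whose Wald interval is unreliable if infections are few; one score interval should be named instead

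*SAP*

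**What the plan says.** - Section 5.2.1 has CLABSI "analyzed by GLM (the same method as the primary outcome", and then: "The difference of incidence and its two-sided 95% CIs between the two groups will be estimated".
- Section 5.1.1 defines the primary method as a GLM with treatment as the fixed effect, "following a binomial distribution and identity link function". Section 3.6 plans that outcome at 55% in the control arm.
- Section 5.2.1 adds an option: "If necessary for analysis, odds ratios or risk differences with two-sided 95% CIs of the two groups will be derived from the GLM". The logit link would serve the odds ratio, and the identity link the risk difference.
- The only convergence rule, in section 5.1.2, begins "If the above identity-binomial GLM does not converge when all covariates are introduced into the model" and removes covariates from the adjusted primary model. The CLABSI model has no covariates to remove.
- Section 5.2.5 allows other methods where thought necessary, but names neither a method nor a trigger.
- Section 5.2 sets the frame: "All secondary outcomes will be analyzed as a superiority design", with two-sided 95% intervals.
- Section 2.2.2 counts only definite cases, which need the same pathogen in two cultures. No expected CLABSI rate is given anywhere.

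**The concern.** A method that suits a 55% outcome need not suit a rare one. A binomial model with an identity link and treatment alone is saturated: it returns the two observed proportions, and its usual interval is the Wald interval. An arm with no events has an estimated variance of zero, so the model treats its rate as known exactly.

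The introduction presents catheter-related bloodstream infection as the serious harm and skin colonization as one of the factors leading to it. The trial tests a longer first dressing interval, so the upper limit for CD7d minus CD24h on CLABSI is its direct figure on infection risk. If that limit is too low, the data appear to rule out an excess that they do not rule out.

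**Working it through.** **Inputs.** 98 evaluable and 140 randomised per arm, 1:1 (sections 3.4 and 3.6); model and interval from sections 5.1.1 and 5.2.1. The CLABSI rates are assumptions, because the SAP gives none. All differences are CD7d minus CD24h, in percentage points.

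**The plan's own figure.** n = (1.960 + 0.842)² × 2 × 0.55 × 0.45 / 0.20² = 97.1, rounded up to 98; 98 / 0.70 = 140. Section 3.6 reproduces.

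**Interval formula.** Difference ± 1.96 × √[p₂(1 − p₂)/n + p₁(1 − p₁)/n], with p₂ for CD7d and p₁ for CD24h. For 3/140 v 0/140 the standard error is √(0.02143 × 0.97857 / 140) = 0.01224, all of it from CD7d. The interval is 2.14 ± 1.96 × 1.224 = -0.26 to 4.54. A fitted identity-link binomial model gave the same limits.

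**Wald against Miettinen-Nurminen (MN), 140 per arm.**

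| Events, CD7d v CD24h | Wald | MN |
|---|---|---|
| 0 v 0 | 0.00 to 0.00 | -2.68 to 2.68 |
| 1 v 0 | -0.68 to 2.11 | -1.98 to 3.94 |
| 3 v 0 | -0.26 to 4.54 | -0.57 to 6.12 |
| 3 v 3 | -3.39 to 3.39 | -4.24 to 4.24 |
| 7 v 7 | -5.11 to 5.11 | -5.62 to 5.62 |

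At 98 per arm, 0 v 0 gives zero width against ±3.79, and 3 v 0 gives an upper limit of 6.47 against 8.64. The gap narrows as events accumulate.

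**Logit option.** With 3 v 0 the fitted log odds ratio was about 21.7 with a standard error of about 18,000. The estimate is infinite in principle, so the option gives no usable interval.

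**How often an arm is empty, equal rates p in both arms.** P(no events in one arm) = (1 − p)ⁿ. At p = 1%, n = 140: 0.99¹⁴⁰ = 0.245. At least one empty arm: 1 − (1 − 0.245)² = 43%. Both empty: 0.245² = 6.0%.

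| Rate | At least one empty, n = 140 | At least one empty, n = 98 | Both empty, n = 140 |
|---|---|---|---|
| 0.5% | 75% | 85% | 24.6% |
| 1% | 43% | 61% | 6.0% |
| 2% | 11.5% | 26% | 0.3% |
| 3% | 2.8% | 10% | below 0.1% |
| 5% | 0.2% | 1.3% | below 0.1% |

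**How often the upper limit falls below the true difference** (exact enumeration of all event counts, n = 140, nominal 2.5%).

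| True rates, CD7d v CD24h | Wald | MN |
|---|---|---|
| 2% v 1% | 6.8% | 1.2% |
| 3% v 1% | 6.8% | 1.6% |
| 4% v 2% | 4.6% | 2.0% |
| 8% v 5% | 3.0% | 2.3% |
| 1% v 1% | 1.3% | 1.3% |
| 2% v 2% | 2.3% | 2.3% |
| 5% v 5% | 2.6% | 2.4% |

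At 98 per arm and 2% v 1%, Wald misses 13.9% and MN 1.1%.

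**The case against.** - **The event rate is assumed.** A reader might infer from the definite-only definition that CLABSI will be rare. Section 2.2.2 gives a definition, not a frequency. This objection stands, and the point holds only if events are few.
- **Total breakdown is narrow.** The zero-width interval needs both arms empty, which is 6.0% at a 1% rate and 0.3% at 2%. With one empty arm the identity model usually still returns an interval, though one that ignores that arm's uncertainty. This stands.
- **The limit is not always too low.** A reader might infer that rarity alone causes undercoverage. It does not: at 1% v 1% the Wald miss rate is 1.3%, better than nominal. The fault needs rare events and a true increase with CD7d. Single data sets also vary: at CD7d 0 v CD24h 5 of 140, the Wald upper limit is -0.50 and the MN limit is lower, at -0.84.
- **Non-significance read as safety.** The superiority frame in section 5.2 invites this inference, but the SAP nowhere says that such a result will be reported as showing no increase. Section 5.2.1 and Table 3 ask for incidences, a difference and its interval. The document does not support the charge.
- **The SAP leaves room for other methods.** It does, in section 5.2.5, but the choice would then be made after the counts are seen. This does not answer the point.

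**Conclusion.** The point holds in conditional form. Section 5.2.1 fixes an interval that is unreliable when CLABSI events are few, and neither the logit option, the convergence rule nor the general permission supplies a working method for an empty arm. At 140 per arm and control rates of 1% to 2%, with about two to three times that rate under CD7d, the upper limit misses a true excess in 4.6% to 6.8% of trials instead of 2.5%. With equal rates, or with about 5% or more per arm, the effect is small.

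This rests on two assumptions: that CLABSI is rare, on which the SAP is silent, and that the GLM's usual Wald interval is the one reported, since the SAP names no other. CLABSI is a secondary outcome, so the non-inferiority conclusion on colonization does not depend on it. It would be too strong to say that the CLABSI analysis will fail, or that the plan equates non-significance with safety.

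**What to change.** In section 5.2.1, replace the GLM and its link options for CLABSI with one method: the risk difference (CD7d minus CD24h) with a Miettinen-Nurminen score 95% interval and the two-sided P value from the matching score test, whatever the event count. With no events in either arm the test statistic is 0/0, so state that P is reported as 1.

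An exact P value should not be paired with this interval, because the two can disagree. At CD7d 5/140 v CD24h 0/140, the MN interval is 0.8 to 8.1 and its score test gives P = 0.024, while Fisher's exact test gives P = 0.06. Fisher's test also lowers power at 3% v 1% (n = 140) to 8%, from 20% with the Wald or score test.

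The cost is a change of SAP wording and a line of code. The interval is somewhat wider when events are few and almost unchanged when they are common. No covariate adjustment is planned for CLABSI, so none is lost.

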5.2.2 Analysis of time-to-event outcomes

The incidence of MARSI will be analyzed as a time-to-event outcome and will be summarized by the number (%) of patients with event by treatment group. The log-rank test will be used to compare the incidence of MARSI, the difference and its 95% CI for the comparison between the two groups will be estimated. Cox proportional hazards regression model will derive hazard ratio and its two-sided 95% CI for comparing two groups. In addition, Cox regression model after adjusting for age, disease type, and CVC catheterization site will also be performed.

5.2.3 Analysis of continuous outcomes

The continuous outcome will be summarized using the number of patients (n), mean, standard deviation (SD), minimum, and maximum by treatment group, and will be analyzed by GLM with treatment as a fixed effect and with normal distribution and identity link function. Differences in the mean outcome and mean differences with their two-sided 95% CIs between two groups will be derived.

5.2.4 Handling of Missing data

Different data imputation methods will be used according to the reasons for the missing data. For randomly missing data, such as vital signs, laboratory indicators, auxiliary examinations, etc., multiple imputations (MI) will be used to impute the missing data for analyses of secondary outcomes.

5.2.5 Analysis of other secondary outcomes

Other statistical methods may be used if deemed necessary.

6.General Considerations for Data Analyses

STATA® (version 16.0) will perform all data analyses and generate most data displays.

SAS (version 9.4) or R may also be used for some data analyses and generating statistical graphs.

6.1 Data Summaries

Continuous variables will be summarized according to the number of patients (n), mean, standard deviation (SD), median, minimum, maximum, and range interquartile (IQR).

Categorical variables will be summarized according to the absolute frequency and percentage of patients (%) by category levels. The denominator for the percentages is the number of subjects in the treatment arm with data available unless noted otherwise.

6.2 Graphical / Table Displays

Figure 1: Patient flow chart. A patient disposition flow chart will be presented showing the number of patients randomized to each treatment arm, reasons for withdrawal, and numbers available for each analysis population.

Table 1. Baseline characteristics of patients

Characteristics	Statistics	CD7d treatment (N=)	CD24h treatment (N=)
Age (year)	Mean(SD)		
Height (cm)	Mean(SD)		
Weight (kg)	Mean(SD)		
Birth weight (kg)	Mean(SD)		
Gender, n (%)	Female		
	Male		
Admission disease diagnosis, n (%)	Congenital heart disease		
	Congenital biliary atresia		
	Tumor		
	Others		
CVC catheterization site, n (%)	Jugular		
	Subclavian		
	femoral		

Table 2. Primary outcome of occurrence of bacterial colonization by treatment

Population	Occurrence of bacterial colonization (95% CI)		Difference (95% CI)	Non-inferiority P value
	CD7d treatment (N=)	CD24h treatment (N=)		

Primary analysis:

ITT population

Sensitivity analysis:

PP population

Adjusted analysis (ITT)^{*}

Adjusted analysis (PP)[#]

* The analysis will be adjusted for age, gender, CVC catheterization site, type of disease, and administration set in the ITT population.

The analysis will be adjusted for age, gender, CVC catheterization site, type of disease, and administration set in the PP population.

Table 3. Summary of generalized linear model analysis of secondary outcomes

Outcomes	Incidence (95% CI)		Difference (95% CI)	P value
	CD7d treatment (N=)	CD24h treatment (N=)		

Incidence of CLABSI**Table 4. Proportion hazards models for time-to-event outcomes**

Outcomes	Incidence (95% CI)		Hazard ratio (95% CI)	P value		
	CD7d treatment (No. of events / No. of patients)	CD24h treatment (No. of events / No. of patients)				
Incidence of MARSI						
Unadjusted analysis						
Adjusted analysis*						

* The analysis will be adjusted for age, disease type, and CVC catheterization site.

7. Study variable list

Variable	Variable interpretation	Variable Type
center	Name of center	Text
center_no	Number of center	Text
name	Initials of subject	Text
id	Study ID of subject	Number
date_start	Date of enrollment	Date
date_end	Date of end	Date
investigator	Initials of investigator	Text
arm	Intervention allocation	Categorical
date_birth	Date of birth	Date
gender	Male / Female	Binary
height	Height at baseline	Continuous
weight	Body weight at baseline	Continuous
birth_weight	Body weight at birth	Continuous
cathete_site	Jugular/ Subclavian/ femoral	Categorical
